Alcohol use disorders (AUD) and PTSD commonly co-occur:^{21, 22} The rates of PTSD among men and women with AUD are at least twice as high as those in the general population,²³ and PTSD afflicts 25-53% of substance use disordered (SUD) patients in treatment.²⁴⁻²⁶ This comorbidity is associated with more severe clinical impairment, shorter times to relapse, more treatment recidivism, overall greater use of treatment services, worse physical health status, and greater treatment costs.^{4, 25, 27-40} Studies of patients with comorbid PTSD and AUD have found that as PTSD symptoms increase, the severity of AUD symptoms also increases,^{41, 42} and that a decrease in PTSD symptoms predicts less alcohol use following

treatment.⁴³ A recent study of Veterans found that alcohol use mediated the relationship between PTSD hyperarousal symptoms and aggression.⁴⁴ Further, patients perceive that their PTSD symptoms contribute to their substance use,³² and that alcohol use temporarily makes their PTSD symptoms better.⁴⁵ In laboratory cue reactivity studies, individuals with co-occurring AUD and PTSD evidence increased alcohol cravings in response to personalized trauma imagery cues,^{46, 47} and alcohol intake has been shown to dampen the physiological stress response and emotional memory of trauma-related stimuli.⁴⁸ Identification of effective treatments, including pharmacological interventions, for this common and debilitating comorbidity would be an important contribution to the welfare of SMs and Veterans.

Elevated noradrenergic activity contributes to the pathophysiology of AUD and PTSD: Human studies demonstrate increased peripheral and CNS noradrenergic activity in persons with AUD and those with PTSD.⁵⁻¹⁰ This increased noradrenergic activity appears to contribute to the pathophysiology of both disorders. In AUD, increased CNS noradrenergic activity enhances alcohol reward/reinforcement and also increases the hyperarousal and anxiety that lower the threshold for stress-induced relapse to heavy drinking.⁴⁹ These two mechanisms likely contribute to the initiation and maintenance of AUD. In PTSD, increased CNS noradrenergic activity likely contributes to nighttime sleep disturbance and trauma nightmares and to daytime hypervigilance, irritability, and increased startle.^{10, 50}

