The proposed study is a 21-week, titration to stable dose, randomized, two-group parallel-design, double-blind, placebo-controlled trial to evaluate the efficacy of prazosin for decreasing alcohol use in 200 active duty Service Members (SMs) who are receiving standard outpatient treatment for AUD at JBLM. Treatment groups will be stratified by presence or absence of PTSD and by assignment to Behavioral Health treatment group, the Moderate Intensity treatment group or the High Intensity treatment group. We are requesting to consent up to 300 Service Members to randomize 200 to study drug to have 120 study completers.

Prazosin is an FDA approved drug that is being used off-label for investigational purposes in this study.

Exemptions for an Investigational New Drug (IND) application to the FDA:

This study will be conducted using the drug, prazosin, which has been approved by the FDA for the following indication(s): treatment of hypertension.

Pursuant to AR 40-7, paragraph 4-12, "Use of an Approved Drug for an Unapproved Indication," this study does not require the acquisition of an IND number from the FDA. All conditions listed in this paragraph as "a-e" are met by this clinical investigation. Additionally, Department of Health and Human Services "Investigational Use of Marketed Products" guidelines, dated February 1989, indicate an IND number is not required in the conduct of this study.

(a) The investigation is not intended to be reported to the FDA as a well-controlled study in support of a new indication for use, nor intended to be used for any other significant change in the labeling for the drugs.

(b) The drugs undergoing investigation are lawfully marketed as prescription drug products, and the investigation is not intended to support any other significant change in the advertising for the drug products.

(c) The investigation does not involve a route of administration or dosage level or use in a patient population or other factor that significantly increases the risks (or decreases the acceptability of the risks) associated with use of the drug products.

(d) The investigation is conducted in compliance with the requirements for human use review and informed consent set forth in AR 40-38.

(e) The drug is not represented in a promotional context as being safe or effective for the purposes for which it is being investigated.

9.6 Target Population:

Describe the population to whom the study findings will be generalized

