drink units per day and binge drinking days throughout the trial, which will serve as primary outcome measures.

- *The Penn Alcohol Craving Scale (PACS)*: A self-report paper-and-pencil instrument that assesses various dimensions of craving for alcohol and has been found to have good reliability and validity.⁸¹ The PACS will be administered at baseline and on weeks 8, 13 and 19, and will be used as a primary outcome measure to determine whether prazosin is associated with reductions in alcohol craving.
- *Alcohol Use Disorders Identification Test (AUDIT)*:⁸² A 10-item self-report questionnaire that has served as a screening instrument for alcohol problems in a number of different settings.⁸³ The AUDIT measures at least two factors, one related directly to alcohol consumption and the other to adverse behavioral effects of excessive consumption.^{84, 85} An advantage of the AUDIT is that it can delineate not just individuals likely to have an alcohol use disorder diagnosis but can place respondents on the full spectrum of alcohol misuse from no problem to hazardous drinking to dependence. The AUDIT has well supported reliability, validity, sensitivity, and specificity. The AUDIT will be modified to inquire about the past year, and will be administered at baseline. The AUDIT will be used to characterize the sample.
- *Clinician-Administered PTSD Scale for DSM-IV (CAPS)*:⁸⁶ The 17-item CAPS uses a structured clinical interview designed to assess the 17 symptoms of PTSD outlined in the DSM-IV. The CAPS will be used by the interviewer to make a current (past month DSM-IV diagnoses of PTSD. The frequency and intensity of each symptom on the CAPS is rated on separate 5-point scales, yielding both dichotomous and continuous scores (range = 0 to 8) for each symptom and for the disorder as a whole (range = 0 to 136). The CAPS will be used as a stratification variable for group assignment and as a secondary outcome measure and will be administered at screen, baseline (to be done at baseline only if more than 14 days has elapsed since the screen visit) and weeks 8, 13 and 19.

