- *Pittsburgh Sleep Quality Index (PSQI)*⁸⁷: A self-report questionnaire assessing sleep quality and disturbances over a 1-month time interval. Nineteen individual items generate seven subscale scores: subjective sleep quality, sleep latency, sleep duration, habitual sleep efficiency, sleep disturbances, use of sleeping medication, and daytime dysfunction. A global score may be obtained by summing the seven component subscales (total score range: 0-21). The PSQI will be used as a secondary outcome measure and will be completed at baseline and weeks 8, 13 and 19.
- *Short Inventory of Problems (SIP)*:⁸⁸ This 15-item self-report questionnaire will be used to assess problems with alcohol, other than alcohol dependence. The SIP has been found to have adequate test-retest reliability and internal consistency. The SIP will be used as a secondary outcome measure to determine whether prazosin is associated with reductions in alcohol-related problems. This self-report instrument will be completed at baseline and weeks 8, 13 and 19.
- *PTSD Checklist-Military (PCL-Military)*:⁸⁹ A well validated 17-item self-report measure assessing severity of PTSD symptoms specifically in the military combat operations context consistent with DSM-IV criteria, with scores ranging from 17 to 85. The PCL-M will be completed at baseline and weeks 8, 13 and 19.
- *Patient Health Questionnaire-9 (PHQ-9)*:⁹⁰ The 9-item depression module of the Patient Health Questionnaire, a self-report version of the PRIME-MD used to diagnose major mental disorders. The PHQ-9 items correspond with DSM-IV criteria for depression, with each item scored from "not at all" to "nearly every day." Items of the PHQ-9 are internally consistent (alpha = 0.86-0.89) and the questionnaire exhibits high test-retest reliability coefficients. Agreement between the PHQ-9 and clinician-based interview diagnosis of major depression is high, with a sensitivity of 88% and a specificity of 88% using a PHQ-9 score ≥ 10 . The PHQ-9 will be completed at baseline and weeks 8, 13 and 19.

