11.0 Statistical/Data Analysis Plan

11.1 Statistical Considerations:

List the statistical methods to be used to address the primary and secondary objectives, specific aims, and/or research hypotheses. Explain how missing data and outliers will be handled in the analysis. The analysis plan should be consistent with the study objectives. Include any sub-group analyses (e.g., gender or age group). Specify statistical methods and variables for each analysis. Describe how confounding variables will be controlled in the data analysis

Primary Outcome Measures: Analysis of the primary outcomes will follow the ITT principal. For each of the two outcomes, a linear regression model with covariates that include treatment group, the stratifying variables, and baseline value of the outcome will be used to compare the prazosin and placebo groups at 13 weeks. In addition, we will conduct a repeated measures analysis using data from the two points of follow-up (8 and 13 weeks). The repeated measure analysis will be conducted by comparing response profiles between prazosin and placebo groups. An initial comparison will be conducted using the general estimating equations (GEE) method of Liang and Zeger,⁹¹ which allows all observed data points for each participant. Secondarily, an analysis of covariance (ANCOVA) rate of change analysis will be done as a confirmatory or sensitivity analysis. Stratifying variables will be included as covariates in each model since they are factors in the stratification. It is anticipated that a retrieved dropout strategy will

result in a limited number of missing observations. For the GEE analysis no imputation strategy is required. For the ANCOVA analysis the missing data patterns will be evaluated between the treatment groups. If the patterns are similar and the magnitude of missing data is small, a conventional last observation carried forward (LOCF) imputation will be performed. If the amount of missing data is substantial and/or the patterns of missingness disparate, as an alternative to the traditional ANCOVA, the summary statistic method of Dawson⁹² will be employed. This method has been shown to be robust to non-ignorable missingness. The approach summarizes the response profile using a least square slope, and stratifies on the missing data pattern. We will also run analyses to assess the interactions between treatment group and gender.

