A completers analyses will be done in a similar fashion for the primary outcome measures, using only the cases that remained on protocol throughout the 13-week study drug period.

Secondary outcome measures: All secondary outcome measures (PSQI, CAPS, PCL-M, SIP, and biological markers) will be analyzed in a manner similar to that described above for the primary outcome measures. (We will also perform exploratory analyses in a similar manner on the CAPS symptom clusters and individual CAPS items to generate hypotheses about differential responsiveness to prazosin for AUD relative to response of individual PTSD symptom clusters/symptoms).

Procedures to minimize missing data: Although all efforts will be made to complete study visits in person, it may be necessary to obtain assessments by telephone. Attempts will be made to reach the participant by telephone. The following actions will be attempted (as appropriate per visit schedule): 1) adverse events will be assessed by telephone, 2) assessments shall be completed by telephone interview with the raters, 3) self-rated measures will be done by mail using prepaid envelopes, and 4) dispensing of study drug shall be done by traceable shipment. No-show, missed visits and actions taken will be documented in the study record.

11.2 Sample Size:

Sample Size Estimation: The power analysis is based on two types of preliminary data: the results of [name] study of prazosin for reduction of alcohol use in persons with AUD without PTSD and the preliminary results of our study of prazosin for combat trauma PTSD in active duty SMs without AUD in which we obtained the PACS. There were 19 completers in [name] pilot study. Standard drink units in the final month of the study drug period were 30.3 ± 32 (mean \pm SD) ($N=10$) in the prazosin group and 62 ± 58 ($N=9$) in the placebo group ($F=1.50$, $p=0.012$). There were 53 completers in the prazosin study for combat trauma PTSD in active duty SMs. The difference (delta) in PACS scores were -2.6 ± 5.8 ($N=27$) vs. -0.3 ± 3.3 ($N=26$) in the prazosin vs. placebo groups, respectively, $t=-1.74$, $p=0.04$ (one-tailed).

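### CAPS and PCL-M yield one treatment effect averaged over participants with and without PTSD, and no estimate in the PTSD stratum is planned

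*Combined protocol and SAP*

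**What the plan says.** The secondary-outcome paragraph of section 11.1 refers back to the primary analysis: "All secondary outcome measures (PSQI, CAPS, PCL-M, SIP, and biological markers) will be analyzed in a manner similar to that described above". That analysis has three relevant features.

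- Population: "Analysis of the primary outcomes will follow the ITT principal".
- Week-13 model: "a linear regression model with covariates that include treatment group, the stratifying variables, and baseline value of the outcome". A GEE analysis of weeks 8 and 13 is added, with the stratifying variables again as covariates.
- Interaction: "We will also run analyses to assess the interactions between treatment group and gender". Section 11.1 names no other.

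Section 9.5 says: "Treatment groups will be stratified by presence or absence of PTSD". Assignment to the Behavioral Health, Moderate Intensity or High Intensity treatment group is the other stratifying factor. Section 10.2 gives CAPS two roles: "The CAPS will be used as a stratification variable for group assignment and as a secondary outcome measure".

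Hypothesis 2 (section 9.4) asks whether PTSD modifies the effect on AUD, not on PTSD symptoms. No section plans a PTSD-stratum estimate, or a treatment-by-PTSD term, for CAPS or PCL-M. The exploratory CAPS cluster and item analyses follow the same approach as the other secondary outcomes.

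**The concern.** The trial enrols people without PTSD by design, and CAPS is the instrument that classifies them. Someone below the diagnostic threshold has less room to fall on scales whose floors are 0 (CAPS) and 17 (PCL-M), so a smaller effect in that stratum is plausible. A stratum covariate lets mean scores differ between strata, but it leaves a single treatment coefficient that averages the two strata's effects in proportion to their size.

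Section 9.3 cites large effects of prazosin on PTSD symptoms in veterans with PTSD, and section 14.4 lists fewer PTSD symptoms as a possible benefit. As planned, the trial would not estimate that effect in the participants who have the disorder. An effect present in PTSD could be reported as small, and its size would depend on a PTSD share that the plan neither fixes nor states.

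**Working it through.** **The plan's own figures.** No power is stated for CAPS or PCL-M. The stated primary-outcome figures were reproduced first, using normal-approximation power, Φ(d·√(n/2) − 1.96), with 60 per arm and root-mean-square SDs.

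- Standard drink units: d = (62 − 30.3)/46.84 = 0.677, power 96.0% (stated 97%).
- PACS: d = 2.3/4.72 = 0.487, power 76.1% (stated 76%).
- Dropout: 120/(1 − 0.40) = 200, as stated.

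**What the pooled model estimates.** With 1:1 allocation within strata, stratum as a main effect and one treatment term, the expected coefficient is approximately

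pooled effect = p·δ + (1 − p)·q·δ,

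where p is the PTSD share, δ the effect in PTSD, and q the non-PTSD effect as a fraction of δ.

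The documents give neither p nor q for this trial. Section 9.3 reports that "PTSD afflicts 25-53% of substance use disordered (SUD) patients in treatment"; this is a background range, used here as an assumption.

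- q = 0: the pooled effect is 25% of δ (p = 0.25), 40% (p = 0.40) or 53% (p = 0.53).
- q = 0.25: 0.25 + 0.75 × 0.25 = 44% of δ (p = 0.25); 0.53 + 0.47 × 0.25 = 65% (p = 0.53).

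**Power with q = 0.** Let the SD be 1 in PTSD and r without PTSD, with n = 60 completers per arm.

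- Pooled: Φ( pδ/√(p + (1 − p)r²) × √(n/2) − 1.96 ).
- Stratum only: Φ( δ × √(np/2) − 1.96 ).

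At p = 0.40 and δ = 0.6:

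- Pooled, r = 1.0: 0.24 × √30 = 1.31, power 26%.
- Pooled, r = 0.5: 0.24/0.742 × √30 = 1.77, power 43%.
- Stratum: 0.6 × √12 = 2.08, power 55%.

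Results for δ = 0.6 and 120 completers:

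| PTSD share | Pooled power (r = 1.0 to 0.5) | Stratum power | Completers in stratum |
|---|---|---|---|
| 25% | 13–24% | 38% | 30 |
| 40% | 26–43% | 55% | 48 |
| 53% | 41–58% | 67% | about 64 |

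At 40% PTSD and δ = 0.8, power is 42–66% pooled against 79% in the stratum. With all 200 analysed and δ = 0.6, it is 40–63% against 77%.

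**When the power advantage disappears.** The two analyses have equal power when p + (1 − p)q = √( p·(p + (1 − p)r²) ). At p = 0.40:

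- r = 1.0: 0.40 + 0.60q = √0.40 = 0.632, so q = 0.39.
- r = 0.5: 0.40 + 0.60q = √(0.40 × 0.55) = 0.469, so q = 0.12.

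Above those values the pooled analysis is the more powerful one, although it still estimates a different quantity.

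**The case against.** The strongest reply is that the all-randomised estimate is a valid randomised answer to another question: the effect on PTSD symptoms in service members with AUD. Both objectives concern AUD, and no power is claimed for CAPS or PCL-M. This stands. The gap is a missing estimate; the planned one is not wrong.

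Four stronger readings are tempting, and the documents do not support them.

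- A reader might infer that the effect is diluted exactly to the PTSD share. That requires zero effect without PTSD. The documents give no CAPS or PCL-M scores for that stratum, and lacking the diagnosis is not the same as scoring near the floor. Section 9.3 links noradrenergic activity in AUD itself to hyperarousal and anxiety, so some effect there fits the protocol's rationale.
- A reader might infer that pooling must cost power. People with little room to improve should also vary little. With p = 0.40, δ = 0.6 and q = 0, pooled power rises to 51% at r = 0.25, against 55% in the stratum.
- A reader might infer that the PTSD stratum should replace the full sample as the main population. That is a debatable choice of estimand. It fits least well for the cluster and item analyses, whose stated purpose is to set PTSD-symptom response against AUD response, and AUD is present in everyone.
- A reader might cite the description of PCL-M as a "self-report measure assessing severity of PTSD symptoms specifically in the military combat operations context", since section 12.5 requires no deployment or combat exposure. That is equally true of participants with PTSD, so a stratum analysis would not address it.

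**Conclusion.** The point holds as a gap in the secondary analysis. Whenever the effect on CAPS or PCL-M is smaller without PTSD, the planned estimate understates the effect in PTSD and depends on who is recruited. This follows from the model and needs no assumption about variances. In the limiting case of zero effect without PTSD, the estimate is 25–53% of the PTSD effect; with a quarter of the effect there, it is 44–65%.

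The power argument is conditional. It rests on an assumed PTSD share, an assumed effect of 0.6 or 0.8 SD, SD ratios of 0.5 to 1.0, and no effect without PTSD. It should not carry the case.

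The all-randomised population for the secondary outcomes is itself inferred, from ITT for the primary outcomes plus the cross-reference; it is the natural reading. The primary outcomes are unaffected.

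**What to change.** In the secondary-outcome paragraph of section 11.1:

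- Keep the all-randomised analysis of CAPS and PCL-M.
- Add a treatment-by-PTSD term for these two scales, with a prespecified prazosin–placebo estimate and confidence interval in the randomised PTSD-present stratum, adjusted for baseline score and treatment-intensity stratum.
- State that this stratum estimate is the one used when reporting the effect on PTSD symptoms in people with PTSD, and that it is reported whatever the interaction test shows.
- Base its interval on the stratum's own residual variance. At 40% PTSD and an SD ratio of 0.5, a common residual SD would be √0.55 = 0.74 of the PTSD-stratum SD, and the interval would be too narrow.
- Leave the exploratory cluster and item analyses in all randomised participants, with PTSD-stratum results alongside.

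The cost is wording only: PTSD is already a stratification factor, so the comparison within the stratum is randomised, and no new data are needed. The downside is precision. With 120 completers the stratum holds about 30 to 64 people. The 95% half-width, 1.96·√(2/n) with n per arm, is then 0.72 SD (n = 15) to 0.49 SD (n = 31.8), against 0.36 SD for 60 per arm at the same SD. It also adds one more secondary comparison.

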These clinical studies were carried out in parallel with rodent studies investigating effects of prazosin on alcohol ingestion. Drs. [name] and [name], in collaboration with Drs. [name] and [name] at the Salk Institute, demonstrated that prazosin treatment decreased operant ethanol self-administration by Wistar rats during acute ethanol withdrawal.⁷⁶ In a second study, conducted in collaboration with [name] at the University of Indiana, they demonstrated that both acute and chronic prazosin treatment decreased ethanol consumption by alcohol preferring "P" rats.⁶⁵ In a study evaluating prazosin effects on rewarding properties of alcohol, we demonstrated that prazosin infusion into the ventral tegmentum blocked alcohol-conditioned place preference in mice (manuscript in preparation).

9.4

Objectives/Specific Aims/Research Questions:

Describe the purpose and objective(s) of the study, specific aims, and/or research questions/hypotheses

The objectives of this study are: 1) determine prazosin efficacy for AUD in Service Members (SMs) who are participating in outpatient AUD treatment and 2) determine if the presence of PTSD affects prazosin efficacy for AUD.

The hypotheses are that: 1) prazosin is more effective than placebo for AUD in these SMs; and 2) prazosin effect size will be greater in SMs with PTSD than without PTSD.

Primary outcome measures will consist of the alcohol use calendar and the Penn Alcohol Craving Scale (PACS). Secondary outcome measures will be the Short Inventory of Problems (SIP), and biological markers of alcohol use (phosphatidyl ethanol [PEth] and gamma-glutamyl transferase [GGT]), and successful completion rate of the alcohol treatment program. PTSD symptoms will be assessed with the Clinician Administered PTSD Scale (CAPS) and the PTSD Checklist-Military (PCL-M). Sleep quality will be monitored by the Pittsburgh Sleep Quality Inventory (PSQI). Depression will be assessed by the Patient Health Questionnaire-9 (PHQ-9). Medication compliance will be monitored with pill counts.

9.5 Study Design:

Describe study design in one to two sentences (e.g., prospective, use of existing records/data /specimens, observational, cross-sectional, interventional, randomized, placebo-controlled, cohort, etc.). Specify the phase – Phase I, II, III, or IV – for FDA-regulated investigational drug research

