We used these preliminary data to power for both the primary outcome measures, the alcohol use calendar (similar to the Time Line Followback from [name] Voice Response [IVR] Standard Drink Units [SDU] data) and the PACS (from [name] data). Using the SDU data gives us 97% power, 2-tailed at $\alpha=0.05$ with a sample size of 60 in each group (total $N=120$). Using the PACS data gives us 76% power, 2 tailed, at $\alpha=0.05$, and 85% power, one tailed, at $\alpha=0.5$, with the same sample size. We have conservatively powered because [name] used IVR methodology and data were from persons with AUD without PTSD, and [name] were from Service Members with PTSD without diagnosed AUD, to power adequately for not only Hypothesis 1 for prazosin efficacy for AUD, but also Hypothesis 2 to determine the effects of PTSD diagnosis on response to prazosin for treatment of AUD.

Assuming an approximately 40% dropout rate, we will randomize 200 participants to have 120 study completers.

11.3 Total number of subjects requested (including records and specimens):

300

11.4 If you are recruiting by study arm, please identify the arms of the study and how many subjects will be enrolled in each arm

randomize 200 on a 1:1 ratio prazosin or placebo

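### Hypothesis 2 (larger prazosin effect with PTSD) has no test in the analysis plan, and 120 completers do not power it adequately

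*Combined protocol and SAP*

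**What the plan says.** Section 9.4 gives two objectives. The second is to find out whether PTSD changes prazosin's efficacy for alcohol use disorder, and its hypothesis is that "prazosin effect size will be greater in SMs with PTSD than without PTSD". The abstract (9.1) says the same. Section 9.5 stratifies randomisation by PTSD and by treatment-programme group.

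Section 11.1 compares the arms at week 13 by linear regression on treatment, the stratifying variables and the baseline value, with GEE and ANCOVA analyses of the repeated measures. On the stratifiers it says: "Stratifying variables will be included as covariates in each model since they are factors in the stratification". The only effect-modification analysis it names is: "We will also run analyses to assess the interactions between treatment group and gender". The rest of 11.1 covers completers, secondary outcomes and exploratory CAPS cluster and item analyses. Section 11.6 covers baseline checks, retention, adherence and adverse events.

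Section 11.2 reports power for 60 completers per arm: "Using the SDU data gives us 97% power"; "Using the PACS data gives us 76% power, 2 tailed"; and "85% power, one tailed". It then says the trial was sized "to power adequately for not only Hypothesis 1 for prazosin efficacy for AUD, but also Hypothesis 2". It gives no interaction size, PTSD share, stratum size or power figure for Hypothesis 2.

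**The concern.** Hypothesis 2 is about a difference between two treatment effects. A main-effect covariate for PTSD lets the outcome level differ between strata but assumes the same treatment effect in both, so it cannot address the hypothesis. Balancing the arms on PTSD at randomisation does not supply a test either.

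Two things are at stake. First, one of the two stated objectives has no planned analysis. Any interaction test added later would be unplanned, with the PTSD definition (CAPS diagnosis, CAPS score or PCL-M) and the model open to choice after the data are seen. Second, because the protocol claims adequate power, a null interaction could be read as evidence that PTSD does not matter when the trial had little chance of detecting a difference.

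**Working it through.** **Inputs (section 11.2).**
- Standard drink units (SDU), final-month totals: 30.3 (SD 32) on prazosin and 62 (SD 58) on placebo. Difference 62 − 30.3 = 31.7; SD = √[(32² + 58²)/2] = 46.84.
- PACS change: −2.6 (SD 5.8) against −0.3 (SD 3.3). Difference 2.3; SD = √[(5.8² + 3.3²)/2] = 4.72.
- 120 completers, 60 per arm, two-sided α = 0.05.
- Assumption: PTSD share p. The documents set no target for this sample. Section 9.3 cites 25–53% for substance-use patients in treatment. I use 50% (most favourable) and 25%.

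**Reproducing the plan's figures.** Overall SE = SD·√(2/60); power = Φ(difference/SE − 1.96).
- SDU: SE = 8.55; 31.7/8.55 = 3.71; power 96.0%. A simple average of the two SDs (45) gives 97.1%. Stated: 97%.
- PACS: SE = 0.861; 2.3/0.861 = 2.67; power 76.1%. Stated: 76%. One-sided at 0.05 gives 84.7%. Stated: 85%, with α misprinted as 0.5.
- 120/(1 − 0.4) = 200 randomised.

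So the stated powers are those of the overall two-arm comparison, that is, Hypothesis 1.

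**Interaction contrast.** This is the treatment difference with PTSD minus the treatment difference without it: SE = SD·√[4/(Np) + 4/(N(1 − p))]. With N = 120 and p = 0.5 this is SD·√(16/120), exactly twice the overall SE: 17.10 for SDU and 1.72 for PACS. Any other split makes it larger.

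| Scenario (two-sided 0.05, no baseline adjustment) | SDU | PACS |
|---|---|---|
| N = 120, 50% PTSD, interaction = main effect | 46% | 27% |
| N = 120, 50% PTSD, interaction = half the main effect | 15% | 10% |
| N = 120, 25% PTSD, interaction = main effect | 36% | 21% |
| N = 120, 50% PTSD, interaction = twice the main effect | 96% | 76% |
| N = 200, 50% PTSD, interaction = main effect | 67% | 41% |

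First row: 31.7/17.10 = 1.85, Φ(1.85 − 1.96) = 0.46; and 2.3/1.72 = 1.33, Φ(1.33 − 1.96) = 0.27. A one-sided 0.05 test, in line with the directional hypothesis, gives 58% and 38%.

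**Detectable interaction at 80% power** (N = 120, p = 0.5): 2.80 × 17.10 = 47.9 drinks over the final month, or 1.5 times the main effect; 2.80 × 1.72 = 4.8 PACS points, or 2.1 times.

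**Completers needed** for 80% power at an interaction equal to the main effect: (1.96 + 0.84)²·SD²·16/difference² = 274.2 for SDU and 528.6 for PACS. That is 275 and 529 completers, or about 457 and 881 randomised at 40% dropout.

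**How large could the interaction be?** The pilot populations in 11.2 set limits.
- The SDU effect of 31.7 was seen in people without PTSD. If the placebo mean is 62 in both strata, the effect with PTSD cannot exceed 62, so the interaction cannot exceed 62 − 31.7 = 30.3. Power there: Φ(30.3/17.10 − 1.96) = 43%.
- The PACS effect of 2.3 was seen in people with PTSD. An interaction above 2.3 would require prazosin to increase craving in those without PTSD. At 2.3, power is 27%.

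**The case against.** The absence of a treatment-by-PTSD analysis is not in dispute. The serious objections concern the power claim.

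- **No interaction size is stated, so the claim is unsupported rather than contradicted.** The percentages do depend on assumed sizes, and an interaction of twice the main effect restores 96% and 76%. But for SDU that means a 63.4-drink reduction with PTSD, more than the pilot placebo mean of 62. For PACS it is still below 80%. The limits set by the pilot populations also point to low power.
- **Baseline adjustment is ignored.** This is fair as a qualification. With an assumed baseline correlation of 0.5, N = 120 gives 57% (SDU) and 34% (PACS); with 0.7, 74% and 46%. With all 200 analysed, SDU reaches 79% and 92%, so the unadjusted 67% is not a ceiling; PACS reaches 51% and 67%. The PACS figures are optimistic because its SD is already that of a change score. Section 11.2, however, rests its claim on 120 completers, where both outcomes stay below 80%.
- **Other pilot measures show larger effects.** Section 9.3 gives drinking days of 5.7 against 0.9 (SEM 1.9, 0.5) and drinks of 20.8 against 2.6 (SEM 6.5, 1.3). Assuming n = 9 and 10, these are about 1.15 and 1.29 SD, and an interaction equal to them would have about 88% and 94% power at N = 120. At half the size it is 35% and 42%. Section 11.2 does not use these data. They also come from people without PTSD, where almost all drinking was already removed: with the same placebo mean in both strata, the interaction in drinking days could be at most 0.9.

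What stands is that the percentages depend on the scenario and should be labelled so.

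**Conclusion.** The concern holds in both parts. The plan as written gives no estimate or test for Hypothesis 2. The statement that 120 completers power it adequately is contradicted by the inputs of 11.2 itself: about 46% (SDU) and 27% (PACS) for an interaction as large as the whole main effect, and about 15% and 10% at half that size.

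These figures assume a 50% PTSD share, a common SD in all cells, the pilot SDs (19 and 53 completers), a normal approximation and no baseline adjustment. An uneven PTSD split lowers them. Baseline adjustment raises them but, up to an assumed correlation of 0.7, not to 80% at 120 completers. The analysis of Hypothesis 1 is not affected.

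**What to change.** In 11.1, add a treatment-by-PTSD term to the week-13 regression and the GEE model, with PTSD defined as it was for stratification. Say which alcohol-calendar measure or measures it applies to, alongside PACS. Report the interaction with its 95% confidence interval and the treatment effect within each PTSD stratum. Keep the Hypothesis 1 test on the model without the interaction.

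In 11.2, delete the adequacy claim for Hypothesis 2. State instead the power or the detectable interaction, with the assumed PTSD share and any assumed baseline correlation. Describe Hypothesis 2 as estimation with a confidence interval; labelling it exploratory would also serve.

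The cost is protocol wording and one extra model term. No additional patients, visits or data are needed. The stated power for Hypothesis 2 becomes less favourable.
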